Study protocol and statistical analysis plan

Validation and Cross-cultural Adaptation of
Croatian SECEL Questionnaire

NCT05346237

October 7, 2021.

Background

Total laryngectomy is surgical removal of the entire larynx and it is performed in cases of advanced larynx cancer, resulting in permanent disconnection of the upper and lower airways, loss of natural voice and difficulty swallowing in some cases. There are three methods of restoring voice after this kind of procedure: electrolaryngeal voice, oesophageal voice or tracheoesophageal voice with voice prosthesis. Verbal communication is very important in everyday life; therefore, it is clear that laryngectomized persons experience an increased feeling of insecurity, depression, psychological and social problems that ultimately reduce the quality of life. The few questionnaires designed for measuring the quality of life of patients with head and neck cancers (e.g., Performance Status Scale for Head and Neck, the Head and Neck Survey, EORTC QLQ-C30 and EORTC QLQ-H&N35) are insufficient, because these questionnaires have resulted in a better understanding of the impact of treatment in head and neck oncology and lack sensitive and important questions about voice and communication dysfunction which is an important issue for laryngeal cancer patients.

Self-Evaluation of Communication Experiences after Laryngectomy (SECEL) questionnaire has been developed, with the aim of evaluating rehabilitation needs and the psychosocial care for patients with laryngeal cancer. This short but comprehensive self-report instrument measures the perceived adjustment to communication experiences and is intended to aid in determining counselling needs in patients with laryngeal cancer who are treated with a laryngectomy. The first aim of this study is to evaluate the translation, psychometric properties and cultural adaptation of a Croatian version of the SECEL questionnaire. Secondary aim is to examine relationship between the Croatian version of the SECEL and the Short Form Health Survey (SF-36) and the Voice Handicap Index (VHI) questionnaires and to examine relationship between objective voice measures and Self-Evaluation of Communication Experiences after Laryngectomy (SECEL:HR).

Design of a research

The research will be designed as prospective observational research, and will include patients who have undergone total laryngectomy, who regularly attended follow-up visits in the ENT clinic and fulfilled the study criteria. Informed consent will be signed. The validation process will be formed according to the guidelines of the World Health Organization for the translation and cross-cultural adaptation of the measuring instrument.

Materials and Methods

Patients who have undergone total laryngectomy and completed minimal their 12-month period without disease after surgery and post-operative treatments such as radiotherapy or chemotherapy will be included in this cross-sectional study. Patients who regularly followed up and have preserved their reading skills. Exclusion criteria will be define considering the absence of any factors which could interfere with data collection (e.g., acute respiratory infection of the upper or lower respiratory tract, presence of neurologic or pulmonary diseases, recurrence of cancer, deviation from the research protocol).

At the first visit all patients included in the study will complete the Croatian version of the Voice Handicap Index (VHI), Short Form Health Survey (SF-36) and Self-Evaluation of Communication Experiences after Laryngectomy (SECEL:HR) questionnaire.

SECEL questionnaire consists of two parts. The first part examines the relevant general data on the person filling out the questionnaire, while the second part consists of 35 items questionably or statement-designed to examine communication experiences. Patients estimates the incidence of these communication difficulties on the Likert scale (0-never, 1-sometimes, 2-often, 3-always). 35 items are grouped according to 3 subscales named General (0-15 score range), Environment (0-42 score range) and Attitude (0-45 score range), and item number 35 is a separate question: "Do you talk the same amount now as before your laryngectomy?" and is rated with a "yes," "more," and "less" rating category. The overall numerical score varies from 0 to 102, and the higher score indicates greater difficulties and worse postoperative speech-communication adjustment. The Voice Handicap Index (VHI) questionnaire consist of 30 items organized in three subscales functional, physical and emotional and also scored with Likert scale with overall score from 0 to 120. Higher scores indicate a greater handicap. The Short Form Health Survey (SF-36) is a multi-purpose short-form health survey that consist of 36 questions divided in eight scales and clustered into two groups: physical and mental health. Each item was standardized (range 0-100), with a higher score representing better QoL. The objective assessment will include the MPT (maximal phonation time) measured in seconds as common clinical measure of glottal efficiency, the DDK (diadochokinesis) of the articulation organs of the 3-syllable "pa-ta-ka" in 5 seconds (rated in syll/s), or how quickly subjects can produce a series of rapid sounds which is a measure of speech efficiency. MPT and DDK of articulation organs are simple tests that can be easily performed in everyday clinical practice. In view of different acoustic outcomes of the alaryngeal speech and due to the lack of specific information on the relationship between the subjective impression of the laryngectomised person and voice measure, it is necessary to perform aerodynamic tests and tests of the articulation organs in order to identify and exclude laryngectomised patients with respiratory and articulation disorders.

All patients will fulfil the SECEL:HR questionnaire twice, two weeks after the initial test and that will be considered as a re-test of the SECEL reliability analysis.

Statistical analysis

Absolute and relative frequencies will be used to represent categorical data. The Shapiro-Willk test will be used to assess the normal distribution of continuous variables. In the case of deviation from the normal distribution, continuous data will be described using the median and interquartile range. The variance of the category variables will be tested using the Fisher's exact test. The differences between three groups of patients (oesophageal, tracheoesophageal speech and electrolarynx) will be tested using the Kruskal-Wall's test (post hoc Conover test). The test-retest reliability will be evaluated with a Pearson's correlation test and 2-way mixed-effects model (consistency definition) intraclass correlation coefficients (ICCs). The correlation between continuous variables will be evaluated by Pearson's correlation coefficient (r). Reliability measurements determined the internal consistency of the items, subscales and the total scores for the SECEL, SF-36 and VHI, by using the Cronbach

Alpha coefficient. All P values will be two-sided. The level of significance will be set to Alpha = 0.05. The analysis will be conduct using the MedCalc® Statistical Software version 20.100 (MedCalc Software Ltd, Ostend, Belgium; <https://www.medcalc.org>; 2022) and the IBM SPSS Statistics 23 (IBM Corp. Released 2015. IBM SPSS Statistics for Windows, Version 23.0. Armonk, NY: IBM Corp.)

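### Maximal phonation time from electrolarynx users is not comparable with that of the other speakers, and a Pearson r pooled over the three voice methods can distort the SECEL:HR–MPT relation in either direction

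*Combined protocol and SAP*

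**What the plan says.** Background defines the operation: "Total laryngectomy is surgical removal of the entire larynx". It lists the ways of restoring voice as "electrolaryngeal voice, oesophageal voice or tracheoesophageal voice with voice prosthesis". Part of the secondary aim is "to examine relationship between objective voice measures and Self-Evaluation of Communication Experiences after Laryngectomy (SECEL:HR".

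Inclusion, under Materials and Methods, covers "Patients who have undergone total laryngectomy and completed minimal their 12-month period without disease after surgery" and makes no distinction by voice method. The same section names two objective measures. One is "MPT (maximal phonation time) measured in seconds as common clinical measure of glottal efficiency"; the other is DDK, in syllables per second. It remarks that alaryngeal speech differs acoustically, but does not say how MPT is to be obtained or read in each voice method.

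Statistical analysis compares "three groups of patients (oesophageal, tracheoesophageal speech and electrolarynx") with a Kruskal-Wallis test, without listing the variables compared. For continuous variables it gives Pearson's r, and it states neither a split by voice method nor an adjustment for it.

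**The concern.** In oesophageal and tracheoesophageal speakers, MPT reflects how long the patient can drive air through a new voice source. With an electrolarynx the tone comes from a device. Its duration in seconds is then a different quantity under the same name. The documents do not describe the device or the timing procedure, so this is an inference from the term electrolaryngeal voice, but a reasonable one.

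If the three groups are pooled, the SECEL:HR–MPT correlation mixes measurements that do not share a meaning. Adjusting for voice method would remove differences in group means. It would leave the non-comparable electrolarynx values inside the within-mode estimate, so this problem is distinct from ordinary confounding by voice method.

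MPT is one of only two objective measures, so a misleading MPT correlation would affect half of the evidence for that part of the secondary aim. Any three-group test of MPT would have the same difficulty.

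**Working it through.** **Inputs.** The documents give no group sizes, mode shares, expected correlation or sample size, so there is no figure of the plan's own to reproduce. Everything below is illustrative. Assumptions:
- Oesophageal and tracheoesophageal speakers are treated as one group, with SD 1 for both MPT and SECEL and within-group correlation r.
- Electrolarynx users are a share p of the sample, with within-group correlation 0 and the same SECEL SD.

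**Check 1: mode means removed.** Let k be the electrolarynx MPT SD divided by that of the other speakers. The pooled within-mode covariance is (1-p)r, the MPT variance is (1-p) + pk², and the SECEL variance is 1. Hence

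r_adj = r(1-p) / √[(1-p) + pk²].

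With r = -0.40:

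| p | k = 0 (electrolarynx MPT hardly varies) | k = 1 | k = 3 |
|---|---|---|---|
| 0.20 | -0.36 | -0.32 | -0.20 |
| 0.30 | -0.33 | -0.28 | -0.15 |
| 0.40 | -0.31 | -0.24 | -0.12 |

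For example, at p = 0.20 and k = 3: -0.32 / √(0.8 + 1.8) = -0.32 / 1.612 = -0.20. At p = 0.40 and k = 0: -0.24 / √0.6 = -0.31.

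**Check 2: no adjustment, which is closer to the plan as written.** Let electrolarynx users differ from the others by dx SDs in mean MPT and dy SDs in mean SECEL, with equal SDs. Then

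r_pooled = [(1-p)r + p(1-p)·dx·dy] / √{[1 + p(1-p)dx²][1 + p(1-p)dy²]}.

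At p = 0.30, p(1-p) = 0.21:

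| dx | dy | pooled r if r = -0.30 | pooled r if r = -0.40 |
|---|---|---|---|
| 0 | 0 | -0.21 | -0.28 |
| +1 | +0.5 | -0.09 | -0.16 |
| +2 | +0.5 | 0.00 | -0.05 |
| -1 | +0.5 | -0.28 | -0.34 |
| -1 | +1 | -0.35 | -0.41 |

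For example, with r = -0.30, dx = -1 and dy = +1: (-0.21 - 0.21) / √(1.21 × 1.21) = -0.42 / 1.21 = -0.35. The relation looks stronger than the -0.30 assumed in the other speakers. With dx = +2 and dy = +0.5 the numerator is -0.21 + 0.21 = 0, so the relation vanishes. Four cases at r = -0.40 and p = 0.30 were also simulated with a million draws each and agreed to within 0.003.

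**Check 3: what restriction costs.** On the Fisher z scale the confidence interval's width is proportional to 1/√(n-3). Dropping a share p widens it by roughly 1/√(1-p): 1/√0.8 = 1.12 at 20% and 1/√0.6 = 1.29 at 40%. Against this, 80% power at two-sided 0.05 for r = -0.40 needs 47 patients. With equal SDs and no mean shift, the pooled analysis needs 75 at p = 0.20, of whom 0.80 × 75 = 60 are other speakers. At p = 0.30 it needs 98, of whom about 69 are. In that scenario restriction loses no power.

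**The case against.** The strongest case on the other side is that the plan is silent rather than committed. The words about all patients attach to the questionnaires, not to MPT. Statistical analysis does not say that the correlation is pooled, and MPT might in practice be recorded as not applicable in electrolarynx users. This stands as a limit on the claim: pooling is inferred from the absence of any restriction. It does not remove the need to specify, because these patients are a named analysis group and nothing excludes them from the MPT analysis.

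A reader might go further in several ways that the documents do not support:
- *Pooling must weaken the correlation.* That follows only once mode means are removed, under the zero-correlation assumption. The plan states no such adjustment, and check 2 shows that the unadjusted r can move either way.
- *Electrolarynx MPT has no upper limit or carries no information.* The documents say nothing about how it would be timed. If testers stopped at a fixed time, values would cluster and the loss would be near the k = 0 column.
- *The reference to glottal efficiency invalidates MPT.* The label does not fit patients without a larynx, but it reads as a general description of the test and changes no analysis. MPT remains meaningful in oesophageal and tracheoesophageal speakers.
- *Respiratory screening fails in electrolarynx users.* Materials and Methods assigns screening to aerodynamic and articulation tests without naming MPT as the respiratory criterion, and it lists pulmonary disease separately as an exclusion.
- *The whole objective-measure aim is lost.* This argument does not touch DDK.

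**Conclusion.** The concern holds in a limited form. MPT in electrolarynx users is not comparable with MPT in the other two groups, the plan does not say how it is handled, and a correlation pooled over the three voice methods can be distorted in either direction.

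The size cannot be fixed from the documents. It depends on the electrolarynx share, on the spread of their MPT, and on differences in group means, none of which is given. Under the assumptions of check 1, a true -0.40 becomes anything from about -0.36 (20% share, almost no spread) to -0.12 (40% share, three times the SD). A small share with little spread would make the issue minor. The consequence is confined to the MPT part of a secondary aim and to any three-group comparison of MPT. The change is worth making because it needs only wording.

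**What to change.** In Statistical analysis:
- Make the main SECEL:HR–MPT correlation the one in oesophageal and tracheoesophageal speakers, reported by mode or adjusted for mode.
- Show electrolarynx MPT separately and descriptively, and leave it out of any three-group comparison of MPT.
- Keep DDK as an objective measure for all three groups.

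In Materials and Methods, describe MPT as the duration of sustained alaryngeal phonation in place of the reference to glottal efficiency.

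No new data are needed. The price is fewer patients in the MPT correlation and a confidence interval wider by roughly 12% to 29% if 20% to 40% of patients use an electrolarynx.

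### Speech groups are compared without regard to time since laryngectomy, so a SECEL:HR difference between modes could partly reflect time since surgery

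*Combined protocol and SAP*

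**What the plan says.** - **Entry.** Under Materials and Methods, patients must have "completed minimal their 12-month period without disease after surgery and post-operative treatments such as radiotherapy or chemotherapy will be included in this cross-sectional study". This is a floor, counted in disease-free time after surgery and post-operative treatment. No ceiling is stated. The exclusion examples are "acute respiratory infection of the upper or lower respiratory tract, presence of neurologic or pulmonary diseases, recurrence of cancer, deviation from the research protocol", and none concerns time since surgery.
- **Allocation.** Design of a research states: "The research will be designed as prospective observational research". Speech mode is observed, not assigned.
- **Outcome construct.** The Background says that SECEL "measures the perceived adjustment to communication experiences". Materials and Methods adds that "the higher score indicates greater difficulties and worse postoperative speech-communication adjustment", on a 0 to 102 scale.
- **Group comparison.** Under Statistical analysis: "The differences between three groups of patients (oesophageal, tracheoesophageal speech and electrolarynx) will be tested using the Kruskal-Wall's test (post hoc Conover test"). No outcome variable is named. The rest of the plan consists of descriptive statistics, the Shapiro-Wilk and Fisher's exact tests, Pearson correlations, the ICC and Cronbach's alpha. There is no regression, stratification, matching or partial correlation.
- **Time since surgery.** It is not named as a variable to collect, report or analyse. The first part of SECEL may hold it ("The first part examines the relevant general data on the person filling out the questionnaire"), but its content is not itemised.

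**The concern.** For a scale of adjustment after an operation, time since that operation is an obvious candidate covariate. With a floor and no ceiling, patients at quite different distances from surgery can enter together, and nothing in the design balances the three speech groups on that distance. Kruskal-Wallis and Conover tests cannot take a covariate. If the groups differ in time and SECEL:HR changes with time, a significant result mixes the two. It could be read as evidence that the questionnaire separates speech modes, or that one mode goes with better adjustment, when part of it is time. A real difference between modes could equally be masked.

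**Working it through.** **No figure to reproduce.** The documents give no sample size, group sizes, SD or effect size. The check is therefore of the text (above) and of how large the problem could be on assumed inputs.

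**Inputs from the documents.** Alpha 0.05, two-sided; three unallocated groups; Kruskal-Wallis test.

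**Assumed inputs.**
- No true mode effect.
- Equal groups of n = 15, 20 or 30.
- SECEL lower by b = 0.3 or 0.4 SD per SD of log time.
- Group means of log time at −d/2, 0 and +d/2, with d = 0.5 or 1 SD between the extremes.

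**Closed-form approximation.** The spurious difference between the extreme groups is b × d, so 0.3 or 0.4 SD at d = 1. With within-group SD 1, the noncentrality of a one-way comparison is

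λ = n × [(bd/2)² + 0 + (bd/2)²] = n b² d² / 2.

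For n = 15, b = 0.3, d = 1: λ = 15 × 0.09 / 2 = 0.675. For n = 30, b = 0.4, d = 1: λ = 30 × 0.16 / 2 = 2.4. The noncentral F with 2 and 3n − 3 degrees of freedom gives the fourth column below. The last column is the simulated Kruskal-Wallis rejection rate (3000 replicates; the standard error at 15% is √(0.15 × 0.85 / 3000) ≈ 0.7 percentage points).

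| b | n per group | λ (d = 1) | F approximation | Kruskal-Wallis, simulated |
|---|---|---|---|---|
| 0.3 | 15 | 0.675 | 10.0% | 10% |
| 0.3 | 20 | 0.90 | 12.0% | 11% |
| 0.3 | 30 | 1.35 | 16.0% | 15% |
| 0.4 | 15 | 1.20 | 14.3% | 13% |
| 0.4 | 20 | 1.60 | 18.0% | 17% |
| 0.4 | 30 | 2.40 | 25.6% | 23% |

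Repeat runs put the lowest cell at 9% and the highest at 24%; about 10–24% is a fair summary. At d = 0.5, λ is a quarter as large (0.169 to 0.60), the approximation gives 6.2% to 9.6%, and simulation gives about 5–10%. With time in the model, rejection was about 4–6%.

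**Second set of assumptions, on the raw scale.** SD 18 points; log-normal time (log SD 0.6, floor 1 year); SECEL lower by 0, 3 or 6 points per doubling of time; 15, 30 or 50 per group; 4000 runs per setting; adjustment by rank ANCOVA on log time.

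| Median years by group | Points per doubling | Unadjusted rejection | Adjusted |
|---|---|---|---|
| 3/3/3 | 0, 3 or 6 | about 5% | about 5% |
| any | 0 | about 5% | about 5% |
| 2/3/5 | 3 | 7–13% | 4–6% |
| 2/3/5 | 6 | 14–41% | 5–6% |
| 2/4/8 | 3 | 10–26% | 5% |
| 2/4/8 | 6 | 27–78% | 5% |

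The last row is extreme. From 2 to 8 years is two doublings, so the spurious gap is about 2 × 6 = 12 points, or 12/18 = 0.67 SD.

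**Reading.** Inflation needs both an imbalance in time and an effect of time. Without either, the error rate is nominal. With both, it grows with sample size. The adjusted rates hold near 5% because time is the only confounder in these simulations and enters the model in the right form, so they show what adjustment can do at best.

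**The case against.** The other side has a good deal of force.

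- **The comparison is not a stated aim.** The Background lists validation and adaptation, and relations with SF-36, VHI and the objective voice measures. No hypothesis about speech modes appears. This stands. A reader might infer that the validation itself is confounded, but Cronbach's alpha, the test-retest ICC and the planned correlations do not rest on this group test.
- **The outcome is inferred.** The Kruskal-Wallis sentence could cover SECEL:HR, VHI, SF-36, MPT, DDK or patient characteristics, even time since surgery. This stands too; SECEL:HR is a reasonable reading because it is the instrument under validation.
- **Neither condition for bias is documented.** A reader might infer that the groups do differ in time, or that SECEL goes on changing after the first disease-free year. The documents show neither. The 12-month floor removes the early period, and the requirement for regular follow-up may narrow the spread.
- **The data may not be in hand.** A reader might infer that time since laryngectomy is already recorded because eligibility depends on it. Eligibility could be checked as a yes/no threshold, possibly from the end of post-operative treatment, so the number has to be asked for.
- **Time is one confounder among several.** Age or radiotherapy could also differ by mode. An adjusted result should not be the sole basis for a claim about modes.

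What the objection does not remove is that the plan specifies an inferential comparison of unallocated groups, with pairwise follow-up, and offers no way to examine a plausible alternative explanation.

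**Conclusion.** The point holds as a possibility, for one ancillary comparison. The open-ended entry window and the lack of any covariate method are plain from the text. If SECEL:HR is the outcome, a difference between modes could partly reflect time since surgery, or be hidden by it. Whether it would in this study is unknown. On assumed inputs with 15 to 30 per group, the false-positive rate is about 5–10% at a 0.5 SD imbalance, hardly a problem, and about 10–24% at 1 SD. The higher rates in the second table need larger imbalances, and the highest also need a steep time effect and larger groups. This is a cheap improvement worth making, not a threat to the core validation.

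**What to change.** 1. Name SECEL:HR total as an outcome of the group comparison, if that is intended.
2. Record time since laryngectomy as a number for every patient and report it by speech mode (median and interquartile range).
3. Keep Kruskal-Wallis with Conover tests as the unadjusted, descriptive comparison.
4. Add one model of SECEL:HR total on speech mode with log(time since laryngectomy) as covariate, fitted on ranks if residuals are clearly non-normal.
5. Report both results together, describe any difference by mode as an association, and state that confounding by other factors remains possible.

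**Cost.** One recorded item per patient, one extra model and a few lines in the Statistical analysis section; no new patients, visits or tests. The model spends one degree of freedom and loses some precision if time and mode are strongly related or the groups are small. If time proves balanced or unrelated to SECEL:HR, the sponsor can say so and this explanation becomes unlikely.

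### The planned SECEL:HR test-retest statistics, Pearson's r and a consistency ICC, cannot show a uniform shift in score between the two administrations

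*Combined protocol and SAP*

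**What the plan says.** For test-retest reliability, the Statistical analysis section names two statistics: Pearson's correlation and a "2-way mixed-effects model (consistency definition) intraclass correlation coefficients (ICCs"). The consistency definition is written out, so nothing has to be inferred.

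The data come from the repeat described at the end of Materials and Methods: "All patients will fulfil the SECEL:HR questionnaire twice, two weeks after the initial test and that will be considered as a re-test".

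The other analyses in the section do not compare the two administrations:
- Fisher's exact test is for categorical variables.
- The Kruskal-Wallis test compares the three speech groups.
- The general Pearson analysis is again a correlation.
- Cronbach's alpha addresses internal consistency: "Reliability measurements determined the internal consistency of the items, subscales and the total scores for the SECEL, SF-36 and VHI".

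No absolute-agreement ICC, paired difference or limits of agreement is planned.

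On use of the score, Materials and Methods says "The overall numerical score varies from 0 to 102, and the higher score indicates greater difficulties", and the Background describes the instrument as "intended to aid in determining counselling needs in patients with laryngeal cancer".

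**The concern.** A test-retest study can go wrong in two ways. Patients may change position relative to one another, or the whole group may move up or down. The planned statistics respond to the first and not to the second. They fall with random error, and the consistency ICC also falls if the spread of scores changes, so the gap is confined to a systematic shift.

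That matters because psychometric properties belong to the first aim and the two-week repeat is the only planned evidence on stability over time. A patient's total is interpreted as a number of points. Evidence that rank order is preserved does not show that a patient would obtain the same total again.

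The two administrations are also described differently. For the first, "At the first visit all patients included in the study will complete the Croatian version of the Voice Handicap Index (VHI"), the SF-36 and the SECEL:HR. Only the SECEL:HR is named for the retest. The first sitting thus includes a further 30 VHI items and 36 SF-36 questions. This does not show that scores will move, but it is a reason to look.

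**Working it through.** The documents give no sample size, SD or target ICC, so there is no planned figure to reproduce. The check has an algebraic part, which needs no assumptions, and an illustration, which does.

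**1. Algebra.** Take n patients and k = 2 administrations. Let MSR be the between-patient mean square, MSC the between-administration mean square and MSE the residual mean square.

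- Consistency ICC = (MSR − MSE) / (MSR + MSE)
- Absolute-agreement ICC = (MSR − MSE) / (MSR + MSE + 2(MSC − MSE)/n)

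Adding a constant to every retest score changes MSC only. MSC is absent from the consistency form, so that ICC does not move. Pearson's r is likewise unchanged when a constant is added to one variable.

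**2. Numerical confirmation.** One simulated sample, n = 50, assumed between-patient SD 15 and error SD 5:

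| Points added to every retest score | Pearson's r | Consistency ICC | Agreement ICC |
|---|---|---|---|
| 0 | 0.907 | 0.905 | 0.905 |
| 5 | 0.907 | 0.905 | 0.874 |
| 10 | 0.907 | 0.905 | 0.765 |
| 15 | 0.907 | 0.905 | 0.627 |

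**3. Size of the gap.** For two occasions with equal SD, agreement ICC = consistency ICC / (1 + d²/2), where d = shift/SD. Assume a consistency ICC of 0.85.

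- SD 18, shift 5: d² = (5/18)² = 0.0772; 0.85/1.0386 = 0.818
- SD 18, shift 10: d² = (10/18)² = 0.3086; 0.85/1.1543 = 0.736

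| Assumed SD | 5-point shift | 10-point shift |
|---|---|---|
| 12 | 0.782 | 0.631 |
| 18 | 0.818 | 0.736 |
| 24 | 0.832 | 0.782 |

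In simulation (4000 datasets, N = 50, SD 18, reliability 0.85), the average consistency ICC was 0.844 at shifts of 0, 5 and 10 points. The average agreement ICC was 0.844, 0.811 and 0.730. With no shift the two agree on average.

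**4. Would the added analysis be informative?** With SD 18 and ICC 0.85, the SD of the differences is 18 × √(2 × 0.15) = 9.86 points. The 95% CI half-width for the mean difference is t × 9.86/√N. The last column is the noncentral-t probability that this CI excludes zero when the true shift is 5 points.

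| Assumed N | Half-width (points) | CI excludes zero |
|---|---|---|
| 30 | 3.7 | 77% |
| 50 | 2.8 | 94% |
| 100 | 2.0 | 99.9% |

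Simulation gave 75.4%, 94.4% and 99.8%. The limits of agreement would lie about 1.96 × 9.86 = 19.3 points either side of the mean difference.

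**The case against.** The strongest reply has five parts.

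- **Exact invariance needs a uniform shift.** Patients near the end of a bounded 0-102 scale cannot all move equally, and a shift that varies between patients partly lowers both planned statistics. This is true, but bounding matters little unless scores pile up at a limit. Simulating rounded scores held within 0-102 (assumed mean 40, SD 18, N = 50) left the average consistency ICC at 0.84 for 5- and 10-point shifts in either direction.
- **Descriptive summaries could reveal a shift.** The plan does describe continuous data, by median and interquartile range if non-normal. Reported for each administration, these would show a change in level informally. The plan does not commit to that or to any comparison.
- **A consistency ICC is a legitimate index.** It is, for rank-order reliability, and it can stay. What is missing is any measure of agreement beside it.
- **Nothing shows that a shift will occur or change a conclusion.** This stands. Patients are at least 12 months disease-free, the documents set no score cut-off or acceptable ICC, and the correlations and group comparisons are unaffected by a uniform shift. In the central illustration a 5-point shift lowers the ICC only from 0.85 to 0.82, well inside a 95% CI of about 0.75 to 0.91 at N = 50. That is an argument for reporting the mean difference as well: at the same N it would detect that shift about 94% of the time.
- **Differences may be skewed.** The plan anticipates non-normal data, and one subscale runs only 0-15. This is fair and is met in the fix.

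**Conclusion.** The concern holds. As written, the plan reports reliability in a form that a uniform shift between administrations cannot affect, and it contains no other comparison of the two. This follows from the formulas and depends on no assumed value.

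The consequence is conditional. If the mean moves, the reported reliability overstates agreement of the raw score: in the illustration, about 0.85 against 0.78-0.83 for a 5-point shift and 0.63-0.78 for a 10-point shift, over assumed SDs of 12 to 24. If the mean does not move, the two ICCs nearly coincide and the added analysis documents that. SD, reliability, N and shift are all assumptions. The change should be made because it is cheap and concerns the only planned evidence on stability; the documents give no evidence that the study's results will be wrong.

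**What to change.** In the Statistical analysis section, amend the test-retest sentence so that, for the SECEL:HR total and each of the General, Environment and Attitude subscales:

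1. the main statistic is the two-way, absolute-agreement, single-measure ICC with 95% CI;
2. the mean test-retest difference is reported with its 95% CI, together with Bland-Altman limits of agreement;
3. if the differences are clearly skewed, the median difference and percentile-based limits are reported as well;
4. the consistency ICC and Pearson's r are kept as supplementary descriptive statistics. The standard error of measurement is optional.

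The cost is SAP wording only. Both administrations are already to be collected, and SPSS and MedCalc are already named. The one drawback is that the headline ICC may be lower than the consistency ICC if a shift exists.

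### Does relying on Pearson's r alone understate the link between SECEL and the objective voice measures if phonation time is skewed?

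*Combined protocol and SAP*

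**What the plan says.** The second part of the secondary aim, in Background, is "to examine relationship between objective voice measures and Self-Evaluation of Communication Experiences after Laryngectomy (SECEL:HR". Under Materials and Methods, "The objective assessment will include the MPT (maximal phonation time) measured in seconds", together with diadochokinesis (DDK) in syllables per second. The SECEL total runs from 0 to 102, and higher is worse.

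The Statistical analysis section sets one method for these associations: "The correlation between continuous variables will be evaluated by Pearson's correlation coefficient (r". The Shapiro-Wilk "test will be used to assess the normal distribution of continuous variables", but its only stated consequence is descriptive: "In the case of deviation from the normal distribution, continuous data will be described using the median and interquartile range". The comparison of the three speech groups is rank-based: "oesophageal, tracheoesophageal speech and electrolarynx) will be tested using the Kruskal-Wall's test (post hoc Conover test". No Spearman or Kendall coefficient and no transformation is named for the correlations. All tests are two-sided at 0.05. The document gives no sample size, expected correlation, standard deviation or skewness.

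**The concern.** The plan expects that some variables may not be normal. It changes the descriptive summaries in that case and uses ranks for the group comparison, yet leaves the correlations on Pearson's r. MPT cannot fall below zero and is measured in patients using three modes of speech, so a long right tail is possible. The aim speaks of a relationship, not a linear one. Materials and Methods also mentions "due to the lack of specific information on the relationship between the subjective impression of the laryngectomised person and voice measure", which can be read as saying that the shape of the relation is unknown.

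If a long tail in MPT, or in both MPT and SECEL, pulled Pearson's r towards zero, the study could report too weak an association or miss it. One sentence adding Spearman's rho as lead coefficient would then look like a cheap improvement.

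**Working it through.** The plan has no figure of its own to reproduce. The inputs from the documents are Pearson's r, two-sided testing and alpha 0.05. Everything else is assumed: n = 50, correlation -0.4, MPT log-normal with log-SD s. The central 95% range of MPT is then exp(3.92 s)-fold: 3.2-fold at s = 0.3, 7.1-fold at 0.5, 23-fold at 0.8.

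**Case A: SECEL linear in log-MPT.** Let Z and E be independent standard normals, MPT = exp(sZ), SECEL (standardised) = -0.4 Z + sqrt(0.84) E.

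- Population Pearson = -0.4 s / sqrt(exp(s²) - 1). At s = 0.3: -0.391. At 0.5: -0.375. At 0.8: -0.32 / sqrt(exp(0.64) - 1) = -0.338. At 1.0: -0.305.
- Population Spearman = (6/π) asin(-0.4/2) = -0.385 for every s, because ranks do not change under exponentiation.

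Spearman's immunity to skew is therefore built into this model.

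**Case B: SECEL linear in MPT seconds.** Let M be the same log-normal MPT, standardised, and SECEL = -0.4 M + sqrt(0.84) E. The relation is again inverse and monotone. Population Pearson is -0.4 for every s. Now Spearman loses, because most patients are crowded at short times where SECEL hardly changes, and ranking discards the information in the long times.

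Simulated power, t-based test, n = 50:

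| MPT log-SD | A: Pearson | A: Spearman | B: Pearson | B: Spearman |
|---|---|---|---|---|
| 0.3 | 82% | 79% | 83% | 76% |
| 0.5 | 79% | 79% | 80% | 69% |
| 0.8 | 73% | 79% | 75% | 55% |
| 1.0 | 68% | 79% | 69% | 44% |

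Spearman minus Pearson, in points:

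- Case A: 79 - 82 = -3; 79 - 79 = 0; 79 - 73 = +6; 79 - 68 = +11.
- Case B: 76 - 83 = -7; 69 - 80 = -11; 55 - 75 = -20; 44 - 69 = -25.

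Mean coefficients at s = 0.8, Pearson v Spearman, are -0.35 v -0.38 in case A and about -0.375 v -0.292 in case B. The same skew makes Pearson the smaller coefficient in one case and the larger in the other. What differs is the scale on which the relation is linear.

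**Size of the case A effect.** The gap in coefficient is 0.38 - 0.35 = 0.03. The sampling SD of r at n = 50 is about (1 - 0.16)/sqrt(49) = 0.12, so the gap is a quarter of one SD. At n = 100 the power gap at s = 0.8 is 97.8 - 95.2 = 2.6 points.

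**Validity.** With no association, Pearson's rejection rate was 0.047 to 0.054. Skew does not inflate false positives.

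**What the documents say about shape.** The words on missing information, read with the rest of their sentence, give the reason for using the tests to identify and exclude patients with respiratory or articulation disorders. They do not address linear versus monotone association. That screening, and the exclusion of pulmonary and neurologic disease, might also narrow the spread of MPT.

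**The case for a change.** The strongest opposing argument is that case A is not far-fetched. Durations often behave better on a log scale, and in case A Pearson does lose 6 to 11 points at log-SD 0.8 to 1.0. With both variables right-skewed the loss is larger: 75% v 79% at log-SD 0.5 each, and 63% v 79% at 0.6 for SECEL and 0.8 for MPT. Bounded SECEL and gamma-distributed MPT show the same pattern, so log-normal tails are not the cause. All of that stands as arithmetic, but each of those models assumes the case A type of dependence, so their agreement does not test it.

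Two limits on the reply should be stated. Case B uses symmetric SECEL errors. If SECEL itself is strongly right-skewed, Spearman can keep an advantage even when the relation is linear in seconds. Case B is also idealised at extreme skew, because SECEL cannot fall below 0. Equally, the 16-point loss (79 - 63) needs an unbounded log-normal SECEL. With SECEL as a bounded item sum of skewness 0.94, the largest loss found was 76.1 - 66.1 = 10 points, again under case A and a 23-fold spread of MPT. Nothing in the documents points to such distributions.

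A further argument is that naming the lead coefficient in advance prevents a choice after seeing the data. The plan already does this: it names one coefficient and ties no switch to the Shapiro-Wilk result. For DDK no loss under Pearson was shown at all.

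**Conclusion.** The concern does not hold. Skew in MPT does not by itself make Pearson's r understate an inverse relation with SECEL or lose power; the shape of the relation decides, and the documents do not give it. At the assumed n = 50 and correlation -0.4, leading with Spearman changes power by between +11 and -25 points over MPT log-SD 0.3 to 1.0 with SECEL or its errors normal. Pearson is ahead or level in both cases up to log-SD 0.5. The potential cost of the switch is thus well beyond the roughly 5 points lost under bivariate normality.

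Pearson's r is pre-specified, holds its error rate and measures a defined quantity, the linear association. Reporting Spearman beside it would be reasonable, but would correct no wrong result. The figures rest on assumed sample size, correlation and distributions. The conclusion needs only that both shapes of relation are compatible with the documents.
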